9.4 Follow-up of AEs and SAEs

After the initial AE/SAE report, the investigator is required to proactively follow each participant at subsequent visits/contacts. All SAEs will be followed until resolution, stabilisation, the event is otherwise explained, or the participant is lost to follow-up (as defined in Section 5.3). Further information on follow-up procedures is provided below.

Follow-up of AEs and SAEs

- The investigator is obligated to perform or arrange for the conduct of supplemental measurements and/or evaluations as medically indicated or as requested by the sponsor to elucidate the nature and/or causality of the AE or SAE as fully as possible. This may include additional laboratory tests or investigations, histopathological examinations, or consultation with other health care professionals.
- New or updated information will be recorded in the originally completed eCRF.
- The investigator will submit any updated SAE data to the sponsor within 24 hours of receipt of the information.

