	 Aged ≥18 years with capacity to consent. Physician-initiated decision to treat with cabozantinib for NET (prior to study enrolment) according to Summary of product characteristics (SmPC) 							
	product characteristics (SmPC). 3. Signed written informed consent.							
	Exclusion Criteria							
	1. Participation in an interventional trial at the same time and/or within 3 months before baseline.							
	2. Contraindication for cabozantinib treatment according to SmPC.							
Study Treatment:	This is a non-interventional study.							
	The medicinal product cabozantinib is prescribed in the usual manner in accordance with the terms of the marketing authorisation.							
	The assignment of the patient to a particular therapeutic strategy is n decided in advance by a study protocol but falls within current pratice and the prescription of the medicine is clearly separated from the decision to include the patient in the study.							
	No additional diagnostic or monitoring procedures are applied to the patients and good pharmaco-epidemiological practices and statistical principles for clinical trials (ICH E9) are used for the analysis of collected data.							

PAGE 6/52

Study Evaluations:

All endpoints will be assessed under real-world conditions.

Primary endpoint

• DCR: proportion of participants who within 6 months achieve complete response (CR), partial response (PR) or stable disease (SD) determined based on radiographic assessments between the date of the first dose of cabozantinib until the date of progressive disease (PD) or date of subsequent therapy.

Disease response definitions:

CR: Complete resolution of all visible disease.

PR: Partial reduction in size of visible disease in some or all areas without any areas of increase in visible disease. Captures a decrease in disease volume even though disease is still present.

SD: No change in overall size of visible disease. Also includes cases where some lesions increased in size and some lesions decreased in size.

PD: Increase in visible disease and/or presence of any new lesions. Includes cases where the clinician indicates PD or progression of disease as the overall assessment.

Secondary Endpoints

- ORR: proportion of participants who achieve CR or PR determined based on radiographic assessments between the date of the first dose of cabozantinib and the date of PD or date of subsequent therapy.
- Patient-reported outcome questionnaire (EORTC QLQ-C30)

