4.3 Study Data Collection

Participants will be treated in accordance with usual medical practice during their participation in this study. No additional assessments or tests will be required by this protocol. This study is non-interventional, thus if some assessments are not routinely performed by the investigator, they will not complete the corresponding sections in the eCRF.

Relevant data collected as part of routine medical care will be captured on an electronic Case Report Form (eCRF). These data will be transmitted to the sponsor for analysis. Data transmitted will be pseudonymized and will be identified by a participant number.

PROTOCOL FINAL V1.0: 30 JULY 2025

PAGE 20/52

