4.4 Study Data Collection Flow

As this is a non-interventional study, treatment with cabozantinib, the nature and timing of study visits and assessments, and data collection at each visit will be conducted as per routine/clinical practice at each clinical site and the SmPC for cabozantinib tablets.

The assessments relevant to this study are presented in Table 4-1. No additional assessments or tests will be required for the purpose of this study.

Table 4-1 Data to be collected in the eCRF

	Collection timepoints (visits)									
		EoS Visit								
		Visit 2	Visit 3	Visit 4	Visit 5	Visit 6	Visit 7	Visit 8	Visit 9 ^a	VISIT FU ^b
Collected data	(Day 1)	(Month	(Month	(Month	(Month	(Month	(Month	(Month	(Month	(approximately 3
		1)	2)	3)	6)	9)	12)	15)	18)	months after cabozantinib treat-
										ment discontinua-
										tion)
Signature of informed consent ^c	X		I	informed o	consent mus	t be signed p	prior to any	documentat	ion of data	
Visit Date	X	X	X	X	X	X	X	X	X	X
Eligibility	X	-	-	-	-	-	-	-	-	-
Demographic and baseline characteristics	X	-	-	-	-	-	-	-	-	-
Significant medical and surgical history	X									
NETs diagnosis	X	-	-	-	-	-	-	-	-	-
Prior systemic treatment for NETs	X	ı	-	-	-	-	-	-	-	-
Prior NETs related radiotherapies	X	•	-	-	-	-	-	-	-	-
Prior NETs related surgeries	X	•	-	-	-	-	-	-	-	-
Tumour assessment ^d	Xe			X^f	Xf	Xf	Xf	Xf	Xf	X ^f
ECOG Performance Status	X	X	X	X	X	X	X	X	Xf	X
Cabozantinib regimen ^g	X	X	X	X	X	X	X	X	X	
Clinical characteristics	X	X	X	X	X	X	X	X	X	
NETs biochemical markers	X	X	X	X	X	X	X	X	X	
EORTC QLQ-C30 and QLQ-GINET21	X	$(X)^h$		X	X	X	X	X	X	
Supporting measures ⁱ	X	X	X	X	X	X	X	X	X	
Concomitant medication for NETs (including concomitant med-	X	X	X	X	X	X	X	X	X	X
ications for AEs)	Λ		Λ	Λ	Λ	Λ		Λ	Λ	Λ
Concomitant non-drug NETs therapy		X	X	X	X	X	X	X	X	
Post-cabozantinib treatment for NETs ^j	-	-	-	-	-	-	-	-	-	X
AEs and Special Situations	X	X	X	X	X	X	X	X	X	X ^k
Study Discontinuation/Completion	-	- X								
Death information form	- X									

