4.8 Participant Information

Prior to enrolment of a participant in this study, the investigator, or a person designated by the investigator, will explain the nature and purpose of this data collection to each participant. As all assessments and procedures will be conducted in accordance with routine/standard clinical practice, participation in the study does not convey any additional risks or burdens for the participant. However, the participant will be provided with information on the benefits and risks of their medical treatment.

Written informed consent must be obtained prior to participant enrolment and prior to any data being entered in the study database. Sufficient time should be allowed to discuss any questions raised by the participant. The participant should be allowed as much time as they need to consider their decision.

The sponsor will provide an informed consent form (ICF), in German language easily understood by the participant. Each participant's original consent form, personally signed and dated by the participant, and by the person who conducted the informed consent discussion, will be retained by the investigator. The investigator will supply all enrolled participants with a copy of their signed informed consent. None of these informed consents will be collected by the sponsor.

The consent form will be revised during the study if important new information becomes available.

PAGE 28/52

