11 ETHICAL CONSIDERATIONS, REGULATORY FRAMEWORK, AND AD-MINISTRATION PROCEDURES

11.1 Ethical and Regulatory Considerations

This study is non-interventional and falls outside the scope of the EU Directive 2001/20/EC [17], the EU Directive 2005/28/EC [18] and International Council for Harmonisation-Good Clinical Practice guidelines.

This study must be conducted in compliance with the recommendations of the Declaration of Helsinki [19] and the International Ethical Guidelines for Epidemiological Studies, Council for International Organizations of Medical Sciences, 2009 [20].

This study complies with the Regulation (EU) 2016/679 of the European Parliament and of the Council of 27 April 2016 on the protection of individuals with regards to the processing of personal data and on the free movement of such data [21].

This study will also follow the recommendations of the International Epidemiological Association Guidelines for the Proper Conduct in Epidemiologic Research [22] and the International Society for Pharmacoepidemiology (ISPE) GPP Guidelines [23].

Safety data collection and reporting should be consistent with EU Good Pharmacovigilance Practice [24] unless dictated by relevant local legislation for safety reporting in which case that must be followed instead.

In addition, this study will adhere to all local regulatory requirements applicable to non-interventional studies.

Before initiating the study, the investigator/institution should have written and dated approval/favourable opinion from the Independent Ethics Committee/Independent Review Board as applicable.

As required by applicable local regulations, the sponsor will ensure all legal regulatory aspects are covered, and obtain approval of the appropriate regulatory bodies, prior to study initiation in regions where an approval is required.

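### Section 9.4 obliges sites to do extra adverse-event tests on sponsor request alone, although the Synopsis and Section 4.3 say nothing is added and Section 4.8 assumes all procedures are routine

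*Protocol*

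**What the plan says.** Section 9.4 deals with what happens after an initial AE or serious AE (SAE) report. The investigator is under an obligation to "perform or arrange for the conduct of supplemental measurements and/or evaluations as medically indicated or as requested by the sponsor", in order to clarify the nature or cause of the event. The section continues: "This may include additional laboratory tests or investigations, histopathological examinations, or consultation with other health care professionals".

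Elsewhere the protocol describes a study that adds nothing to routine care:

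- Synopsis, Study Treatment: "No additional diagnostic or monitoring procedures are applied to the patients".
- Section 4.3: "No additional assessments or tests will be required by this protocol".
- Section 4.4, in connection with Table 4-1: "No additional assessments or tests will be required for the purpose of this study".
- Section 4.8 gives a reason, "As all assessments and procedures will be conducted in accordance with routine/standard clinical practice", and draws a conclusion from it: "participation in the study does not convey any additional risks or burdens for the participant".

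**The concern.** The first trigger in 9.4, medical indication, fits a non-interventional study, because a physician would order such tests anyway. The second trigger, a sponsor request, stands on its own and is binding. Under it a site could have to carry out a test, possibly an invasive one, that the treating physician does not consider indicated.

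A site receiving such a request would have two incompatible instructions: do it (9.4), or nothing is added (Synopsis, 4.3). The participant would undergo a sponsor-driven procedure in a study whose statement on risk and burden assumes that this cannot happen. Section 11.1 also relies on the non-interventional character of the study to place it outside the EU clinical trial directives and ICH-GCP, so the wording should not leave that character in doubt.

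**Working it through.** No arithmetic applies. The check is a comparison of texts.

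**1. Is the 9.4 duty mandatory, and what triggers it?** It is worded as an obligation. The two triggers are joined by *or*, so either suffices. The stated purpose (clarifying nature or causality) limits why an evaluation is done, but it does not bring back a requirement of medical indication.

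**2. Does it reach procedures on the patient?** Yes. The examples include further laboratory tests and histopathology. Consulting colleagues is also listed and would not conflict with anything; nor would passing on results that already exist. The conflict is confined to sponsor-requested tests beyond routine care.

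**3. Which statements does it contradict?**

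- *Synopsis*: excludes additional diagnostic or monitoring procedures on patients, with no exception. Direct conflict.
- *Section 4.3*: excludes additional tests required by the protocol. Section 9.4 is part of the protocol, and an obligation is a requirement. Direct conflict.
- *Section 4.8*: its conclusion depends on the premise that all procedures are routine. A test done only because the sponsor asked makes the premise untrue. Indirect conflict.
- *Section 4.4*: similar to 4.3, but tied to Table 4-1 and to the purpose of the study. Weaker, and not counted.

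The count is therefore two direct contradictions and one undermined premise.

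**4. Does any other text reconcile them?**

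- *Section 5.3* mentions routine management only to explain why there are no withdrawal criteria.
- *Sections 6.2.1 and 9.2.1* apply the rules for non-interventional studies to collecting and reporting AEs, not to working them up.
- *Section 9.5* gives the sponsor a duty to notify authorities, not a right to new tests.
- *Section 11.1* has a general commitment that "this study will adhere to all local regulatory requirements applicable to non-interventional studies", and a sentence on Good Pharmacovigilance Practice that covers safety data collection and reporting. Neither qualifies 9.4.
- *Section 4.5*, by contrast, limits the examination, laboratory and ECG findings reportable as AEs to those from routine practice. The protocol writes the routine-care limit there; 9.4 has none.

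**5. How far does the clause reach?** It covers any AE or SAE in the 150 planned participants. All AEs, related or not, go into the eCRF (9.2.1). SAEs, related nonserious AEs and special situations also go to sponsor pharmacovigilance (9.2.2). The protocol gives no expected frequency of requests, so no rate can be calculated.

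**The case against.** The best defence is that the texts address different things: the Synopsis and 4.3 describe planned data collection, while 9.4 describes follow-up triggered by a safety event and bounded by the aim of explaining it. Section 4.3 does sit under a data-collection heading, and its next sentence is about leaving eCRF sections blank. The examples in 9.4 are permissive, and a request might be met by consultation alone. Section 11.1 has a safety-specific sentence giving local safety legislation precedence. The consent form is not available, so what participants are actually told about AE follow-up cannot be checked.

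Part of this stands. Not every sponsor request would produce a conflict, and the effect on participant information is visible only through 4.8. But the narrow reading is not written down. Section 4.3 speaks of the protocol as a whole, the Synopsis of procedures on patients, and 4.8 of all procedures. The precedence rule in 11.1 concerns collection and reporting, not new tests.

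A second objection is that the proposed wording touches the medical-indication trigger, which is sound, and may cost the sponsor some AE detail in a study with safety among its secondary objectives. That cost is real but small, because the sponsor keeps other routes to information.

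**Conclusion.** The concern holds. As written, the sponsor-request trigger in 9.4 contradicts the Synopsis and 4.3 and removes the premise of 4.8, and nothing in the protocol resolves this. It is a minor point that should be corrected. It bears on internal consistency and participant burden, and it changes neither the disease control rate nor any other estimate.

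The conclusion rests on reading *or* as giving two separate triggers and on taking the statements in the Synopsis and 4.3 as unqualified, which is how they are worded. Actual harm would require the sponsor to request a test that is not indicated.

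**What to change.** In the 9.4 bullet, replace the two-trigger phrase with: *as the treating physician judges medically indicated in routine practice*. Then add: *The sponsor may request existing results and documentation from routine care, or ask the investigator to consider whether further evaluation is medically indicated.*

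The Synopsis and Sections 4.3, 4.4 and 4.8 can then stand unchanged. The sponsor keeps follow-up of AE reports with the investigator (9.2.2), redacted medical records on request (9.3), updated SAE data within 24 hours (9.4) and its notification duties (9.5).

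A shorter alternative is to keep the sponsor request but confine it to routine care. That removes most of the conflict, but leaves open whether a test of a routine kind that is not indicated for this patient could still be required.

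The cost is one bullet at the next amendment, with no extra data or participants. The downside is possibly less detail on an AE where the treating physician sees no need for further evaluation.

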9.5 Regulatory Reporting Requirements for SAEs/Related AEs

- Prompt notification by the investigator to the sponsor of a SAE/related AE is essential so that legal obligations and ethical responsibilities towards the safety of participants.
- The sponsor has a legal responsibility to notify both the local regulatory authority and
 other regulatory agencies about the safety of any medicinal product. The sponsor will
 comply with country-specific regulatory requirements relating to safety reporting to the
 regulatory authority, Institutional Review Boards (IRB)/Independent Ethics Committees
 (IEC), and investigators.
- An investigator who receives an investigator safety report describing a SAE or other specific safety information (e.g. summary or listing of SAEs) from the sponsor will review and then file it in the investigator's site folder and will notify the IRB/IEC, if appropriate according to local requirements.

9.6 Expectedness of Events

The expectedness of an AE shall be determined by the sponsor according to the SmPC) or package insert (PI) for an authorised medicinal product that is being used according to the terms and conditions of the marketing authorisation. If the product has marketing authorisations in several countries with different SmPCs or PIs, one will be selected by the study team as the reference document for assessing expectedness and agreed by the pharmacovigilance Ipsen representative.

The reference document for assessing expectedness of AEs/event in this study will be the current EU SmPC.

PAGE 46/52

10 STUDY MANAGEMENT

10.1 Monitoring Procedures

The investigator is responsible for the validity of all data collected at the site.

Ipsen or Service provider (SP)-assigned monitors may conduct site visits. The investigator will allow direct access to all relevant files (for all participants) and for the purpose of verifying entries made in the eCRF, and assist with the monitor's activities, if requested. Adequate time and space for monitoring visits should be made available by the investigator.

The site must complete the CRFs within 14 days of the participant's visit and on an ongoing basis to allow review by the study monitor, both remotely via the internet and during site visits.

Whenever a participant name is revealed on a document required by the sponsor, the name must be blacked out permanently by the site personnel annotated with the participant number as identification.

10.2 Recording of Study Data

In compliance with Good Pharmacoepidemiology Practices (GPP), the medical records/medical notes, etc. should be clearly marked and permit easy identification of a participantion in this study.

Participant-completed questionnaires will be completed on a paper questionnaire or electronically as per treatment routine at Visits 1, 4, 5, 6, 7, 8 and 9 and captured in the eCRF by the investigator or delegate. Electronic Case Report Form (eCRF) will be utilised for collecting participant data. The sponsor will ensure that the entrusted SP uses adequate technology to ensure data security transfer & backup.

Each site is required to have a computer and internet connection available for site entry of clinical data. To ensure confidentiality and security of the data, usernames and passwords will be used to restrict system access to authorised personnel only, whether resident within the investigator's sites, Ipsen or third parties.

Data entry in the eCRF will be performed by the investigator or by the designated person from his/her team.

10.3 Data Verification on Site

Within the framework of a non-interventional study, only the following source data verification will be performed by the sponsor or SP:

Definition for source data and source documents are given below:

Source Data:

All original records and certified copies of original records of clinical findings, observations, or other activities necessary for the reconstruction and evaluation of the study. Source data are contained in source documents (original records or certified copies).

PAGE 47/52

Source Documents:

Original documents, data and records (e.g. hospital records, clinical and office charts, laboratory notes, memoranda, participant's diaries or evaluation checklists, pharmacy dispensing records, recorded data from automated instruments, copies or transcriptions certified after verification as being accurate copies, microfiches, photographic negatives, microfilm or magnetic media, X-rays, participant files, and records kept at the pharmacy, at the laboratories and at medico-technical departments involved in the clinical study).

The sponsor assigned monitor must verify, by direct reference to the medical records/medical notes, that the data required by the protocol are accurately reported on the eCRF.

The medical records/medical notes must, as a minimum, contain the following: a statement that the participant is included in the study (with corresponding study number).

The participant must have consented to their medical records being viewed by sponsor-authorised personnel, and by local, and possibly foreign, CAs. This information is included in the ICF.

10.4 Data Quality

The eCRF data will be reviewed for completeness, consistency and protocol compliance.

Data consistency and accuracy will be enabled by real-time checks running at time of data entry in the eCRF. Any queries and items not adequately explained will require additional queries to be raised to the investigator for clarification/correction. The investigator must ensure that queries are dealt with promptly. All corrections on the eCRF data will be automatically tracked and a reason for change is always required. In the eCRF, the audit trail function will allow the changes and clarifications made to be viewed.

The investigator must, as a minimum, provide an electronic signature (e-signature) to each eCRF to attest to the accuracy and completeness of all the data. This electronic signature consists of an individual and confidential username and password combination. It is declared to be the legally binding equivalent of the handwritten signature.

10.5 Data Management

Data management will be conducted by a SP, directed by the Sponsor's Medical Affairs Biometry department. All data management procedures will be completed in accordance with Ipsen and the contracted SP SOPs.

The sponsor will ensure that an appropriate eCRF is developed to capture the data accurately. At the study end, the investigator will receive their data, from the clinical study, in an electronic format which will be an exact copy of the eCRF for archiving purposes and future reference.

